6.4 DISCONTINUATION FROM STUDY TREATMENT

Patients will be discontinued from study treatment for any of the following reasons:

- Disease progression
- Intolerable toxicity related to study drug
- Patient requests to withdraw consent or discontinue treatment
- Pregnancy
- Inability of the patient to comply with study requirements
- Conditions requiring therapeutic intervention not permitted by the protocol
- Non-compliance/lost to follow-up
- Investigator discretion
- Discontinuation of the study by the Sponsor

Patients who discontinue from study treatment (for reasons other than progressive disease) will continue to be followed for progression. **Every attempt to continue to follow the patient for progression should be made.**

After withdrawal from protocol treatment, patients should be followed for AEs for 30 calendar days after their last dose of either study drug. All new AEs occurring during this period must be reported and followed until resolution, unless, in the opinion of the investigator, these values are not likely to improve because of the underlying disease. In this case the investigators must record his or her reasoning for this decision in the patient's medical records and as a comment on the electronic Case Report Form (eCRF).

All patients who have CTCAE Grade 3 or 4 laboratory abnormalities at the time of withdrawal should be followed until the laboratory values have returned to Grade 1 or 2, unless in the opinion of the investigator, it is not likely that these values are to improve because of the underlying disease. In this

UTX-IB-301

case, the investigator must record his or her reasoning for making this decision in the patient's medical records and as a comment on the eCRF.

UTX-IB-301

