11.10.2.1.2 DURATION OF RESPONSE

The Duration of Response (DOR) is defined as the interval from the first documentation of CR or PR to the earlier of the first documentation of disease progression or death from any cause. The DOR rate will be compared between treatment groups at the 5%, two-sided statistical significance level using an ANOVA model with treatment effect.

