11.10.2.1.6 PROGRESSION-FREE SURVIVAL

Progression-free survival is defined as the time from the date of randomization until the date of first documentation of definitive disease progression or date of death from any cause, whichever occurs first. Patients who die without a reported prior progression will be considered to have progressed on the day of their death. Patients who did not progress or are lost to follow-up will be censored at the day of their last tumor response assessment. If no baseline or post-baseline assessment is available, the patient will be censored at the date of randomization. If death or PD occurs after 2 or more consecutive missing tumor response assessments, censoring will occur at the date of the last response assessment prior to the missed assessments. The use of a new anticancer therapy prior to the occurrence of PD will result in censoring at the date of last tumor response assessment prior to initiation of new therapy.

This variable will be analyzed via Kaplan-Meier methodology. The median PFS will be estimated for each arm, however no formal hypothesis testing will be conducted.

UTX-IB-301

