3.1 STUDY DESIGN

This study is a fixed-dose, randomized, two-arm Phase 3 trial to assess the efficacy and safety of ublituximab in combination with ibrutinib compared to ibrutinib alone in patients with CLL who have received at least one prior standard treatment regimen and who have at least one high-risk cytogenetic abnormality (17p deletion, 11q deletion, and/or P53 gene mutation).

Following screening, patients meeting the inclusion/exclusion criteria will be randomized in a 1:1 ratio to one of the following treatment regimens:

- Arm A: Ublituximab + ibrutinib
- Arm B: Ibrutinib

Randomization will be stratified according to prior lines of therapy (1 prior vs. 2 or more prior lines of therapy)

All study patients will be evaluated for response after cycles 2, 4, and 6, then every 3 cycles thereafter if patient is on active treatment, or approximately every 3 months thereafter if patient is in follow up. The best clinical response as well as disease progression will be determined by an Independent Review Committee (IRC).

Patients will continue treatment until the occurrence of definitive disease progression, unacceptable toxicity, or withdrawal from the study due to investigator decision or other reasons. Patients who discontinue study treatment for reasons other than disease progression will continue to be followed for progression and/or survival approximately every 3 months.

Upon first assessment scan of the last randomized patient, and site submission of all required efficacy and safety data, the independent DSMB will review the primary and secondary efficacy analyses, and safety data.

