6.2 ANALYSIS METHODS: DOR AND PFS

The date of definitive progression will be the timepoint at which progression is first identified and confirmed by the independent radiographic committee. Death following the discontinuation of study drug will be considered as an event for the DOR and PFS calculation. Data will be censored on the date of the last tumor assessment (including assessments with a Not Evaluable (NE) outcome) for patients who:

- Start alternative anti-tumor therapy prior to disease progression
- Do not have disease progression within 30 days after discontinuation of study drug(s)

TG Therapeutics, Inc. UTX-IB-301 SAP

secondary outcomes will be tested:

If the primary efficacy analysis of ORR is statistically significant for the ITT population, the following

- Complete response rate
- Duration of response
- · Time to response

For each of these outcomes, ublituximab + ibrutinib will be compared to ibrutinib. The Hochberg approach will be used to control the type I error rate. The null hypotheses state that the secondary outcomes do not differ between ublituximab + ibrutinib and ibrutinib. The three p-values associated with these three secondary outcomes are denoted p_1 , p_2 , and p_3 . The ordered p-values, from largest to smallest, are denoted $p_{(1)} \ge p_{(2)} \ge p_{(3)}$. Specifically:

- If $p_{(1)}$ is less than 0.05, all three null hypotheses will be rejected.
- Otherwise, if $p_{(2)}$ is less than 0.025, the null hypotheses associated with $p_{(2)}$ and $p_{(3)}$ will be rejected.
- Otherwise, if $p_{(3)}$ is less than 0.0167, the null hypothesis associated with $p_{(3)}$ will be rejected.

If the primary efficacy analysis of ORR is not statistically significant, the secondary efficacy variable defined above will not be formally conducted.

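### SAP 6.2 censors DOR and PFS unless progression is seen within 30 days of stopping study drug, which contradicts the PFS rules elsewhere and does not fit the DOR definition

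*SAP*

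**What the plan says.** SAP 6.2 gives one set of rules for DOR and PFS. "Data will be censored on the date of the last tumor assessment (including assessments with a Not Evaluable (NE) outcome")) for two groups: patients who start other anti-tumor therapy before progression, and patients who "Do not have disease progression within 30 days after discontinuation of study drug(s"). The same paragraph treats death differently: "Death following the discontinuation of study drug will be considered as an event for the DOR and PFS calculation".

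The other visible rules have no 30-day limit:

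- **PFS.** Protocol 11.10.2.1.6 states: "Patients who did not progress or are lost to follow-up will be censored at the day of their last tumor response assessment". It also censors for new anticancer therapy, for two or more consecutive missed assessments, and for a missing baseline or post-baseline assessment. SAP 6.1.2.5 repeats these rules. SAP Table 3, which is titled for PFS, scores disease progression as an event on its date. It censors after treatment discontinuation only when there is no progression per IRC.
- **DOR.** Protocol 11.10.2.1.2 gives this definition: "interval from the first documentation of CR or PR to the earlier of the first documentation of disease progression or death from any cause". SAP 6.1.2.2 uses the same one. Neither section states a censoring rule.
- **Follow-up.** SAP 3.1 and Protocol 6.1 state: "Patients who discontinue study treatment for reasons other than disease progression will continue to be followed for progression and/or survival approximately every 3 months". Protocol 6.4 adds: "Every attempt to continue to follow the patient for progression should be made".

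**The concern.** A patient who stops drug for toxicity and has IRC progression at a follow-up scan 90 days later is a PFS event under Table 3 and censored under 6.2. The SAP does not say which rule governs. The trial is open label (SAP 3.6), so this choice should not be left until the analysis is programmed.

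The endpoints differ in standing. DOR is compared by a stratified log-rank test at the 5% two-sided level. If ORR is significant in the ITT population, DOR enters a Hochberg family with CR rate and time to response. PFS is outside that family. SAP 6.1.2.5 gives it a stratified log-rank test and allows a later analysis, whereas Protocol 11.10.2.1.6 says: "The median PFS will be estimated for each arm, however no formal hypothesis testing will be conducted".

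If the bullet is applied, progressions that the protocol requires sites to look for are left out of a formally tested endpoint. The censoring may also be informative, most plausibly where drug is stopped on suspected progression that the IRC has not confirmed.

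**Working it through.** The visible text gives no event count or power for DOR or PFS, so there is no plan figure to reproduce. The check compares the rules and then compares the 30-day window with the scan schedule.

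**1. IRC progression found more than 30 days after stopping drug (no new therapy, no missed scans)**

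| Source | PFS | DOR |
|---|---|---|
| Protocol 11.10.2.1.6; SAP 6.1.2.5 and Table 3 | Event | Not covered |
| Protocol 11.10.2.1.2; SAP 6.1.2.2 | Not covered | Event by definition; no censoring rule |
| SAP 6.2 | Censored | Censored |

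For PFS, two explicit rules give opposite answers. For DOR, one censoring rule does not fit the definition.

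**2. Chance that the next scheduled scan falls within 30 days of stopping**

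Inputs are scans after cycles 2, 4 and 6 (28-day cycles, so 56 days apart), then every 3 cycles (84 days), or every 3 months in follow-up (about 91 days), each with a +/- 7 day window (Protocol 8.6, 10 and Table 2). Assume the stop date is uniform within an interval of T days. The chance is 30/T, and moving the scan by 7 days gives (30 - 7)/T to (30 + 7)/T.

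- Cycles 1-6: 30/56 = 54% (41% to 66%)
- After cycle 6, on-treatment grid: 30/84 = 36% (27% to 44%)
- 3-month grid: 30/91 = 33% (25% to 41%)
- Stop at a scan, or 3-month clock restarted at discontinuation: 0%

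The second scan after stopping is always too late. Even if both scans use their windows, the gap is at least 91 - 14 = 77 days in follow-up, or 56 - 14 = 42 days on the 8-week grid. Both exceed 30.

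**3. Share of post-discontinuation progressions that would count**

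These inputs are assumed: exponential time from stopping to progression with rate L = ln 2/median, first scan uniform over T days, then scans every 91 days, and 24 months (730 days) of follow-up. The chance of detection by day 30 is [30 - (1 - exp(-30L))/L]/T. This is divided by the chance of detection by 24 months.

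| Median after stopping | Detected by day 30 (T = 84) | Detected by 24 months | Share counted |
|---|---|---|---|
| 6 months | 2.0% | 92% | 2.1% |
| 12 months | 1.0% | 73% | 1.4% |
| 24 months | 0.5% | 48% | 1.1% |
| 36 months | 0.34% | 35% | 1.0% |

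With T = 56, the numerator is multiplied by 84/56 = 1.5 and the denominator barely changes, so the share is about 1.5% to 3%. If the clock restarts at discontinuation, it is 0%. At the other extreme, if every patient already had progressive disease when drug was stopped, the share would equal the chance in step 2: 36% after cycle 6 and 54% before. An unscheduled scan within 30 days would also raise it.

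**4. Scale for DOR (illustration; every input assumed)**

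Take 48 responders per arm (80% of 60), median DOR 36 months with 20% of the hazard being death, 5% to 15% per year stopping without IRC progression, hazard multiplied by 1 to 2 after stopping, and 0% to 50% of stoppers starting new therapy first. Progressions dropped per arm are then 0.03 to 0.3 of about 5 events at 6 months of DOR follow-up, 0.3 to 3 of 16 to 19 at 24 months, and about 1 to 7 of 25 to 32 at 48 months.

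**The case against.** The strongest reply is that the contradiction is explicit only for PFS, the endpoint outside the Hochberg family. For DOR the other sections are silent on censoring, so 6.2 supplements them and could be read as a deliberate on-treatment rule. The first half stands: a reader might infer that the plan gives two competing DOR censoring rules, and the visible text does not. The second half is weak, because the SAP never describes DOR as an on-treatment measure and 6.2 itself counts deaths after drug is stopped.

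A second reply is that continued scanning is compatible with censoring the later scans in one analysis. That is correct. The follow-up requirement shows that the data are intended and available; it does not make the rule a protocol violation.

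A third is that the bullet only describes patients who never progress. Table 3 already covers them, and on that reading the 30 days would have no function.

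A reader might also infer that every patient without progression within 30 days is lost as an event, or that a scan rarely falls in the window. Neither holds in full: deaths still count, and during cycles 1-6 the next scan is inside the window about half the time. Finally, the SAP contents list shows headings after 6.2 whose text is not visible, so statements about other sections cover visible text only.

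**Conclusion.** The concern holds. For PFS, SAP 6.2 contradicts SAP 6.1.2.5, Table 3 and Protocol 11.10.2.1.6. For DOR, it is the only visible censoring text and does not fit the endpoint's definition. If 6.2 is applied, most progressions arising after discontinuation would not be counted: 97% or more under the constant-hazard assumptions above, and fewer if drug is often stopped when disease is already progressing.

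The consequences are limited. ORR does not use the rule. SAP 6.1.2.5 expects most patients not to have progressed at the ORR analysis, so few DOR events should be affected then. The effect grows at later analyses.

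A reader might infer that the rule favors one arm. The documents do not support that, because they give no discontinuation rates. In the step 4 illustration, equal stopping rates leave the DOR hazard ratio unchanged. At 48 months, stopping at 5% per year in Arm A and 15% in Arm B multiplies it by 1.05 to 1.18, and the reverse by 0.85 to 0.95. The largest shifts on the log scale (ln 1.18 = 0.17, ln 0.85 = -0.16) are below the standard error of 2/sqrt(57) = 0.26. Size and direction therefore remain undetermined. The reasons to act are the inconsistency and the avoidable loss of events.

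**What to change.** Before database lock, amend SAP 6.2:

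1. Delete the 30-day bullet.
2. State that IRC-confirmed progression, on or off study drug, is an event for both DOR and PFS.
3. State that the Table 3 censoring rules apply to DOR as well as PFS: no progression, last tumor assessment; new anticancer therapy, last assessment before it; two or more missed assessments, last assessment before them.

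The third item is needed because deletion alone would leave responders who stop drug and never progress with no stated DOR censoring date, and the missed-assessment rule is visible only for PFS.

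The cost is one bullet removed and two sentences added. The scans are already scheduled, and neither the protocol nor Table 3 needs to change. Deletion also avoids having to decide whether stopping one of the two drugs in Arm A, which Protocol 8.4.1 allows, starts the 30 days. The downside is that progressions found long after stopping drug also reflect time off treatment.

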3.4 UBLITUXIMAB IN COMBINATION WITH IBRUTINIB

Both ublituximab and ibrutinib target, deplete, and inhibit the proliferation of B-lymphocytes through separate and non-overlapping mechanisms of action. Ongoing Phase 3 studies are evaluating therapeutic regimens consisting of other, non-glycoengineered or ADCC optimized, anti-CD20 antibodies in combination with ibrutinib or other kinase inhibitors targeting related pathways, with early signs of tolerability and promising clinical activity.

Consequently, a Phase II study was undertaken to establish the safety and preliminary efficacy of the combination of ublituximab and ibrutinib in patients with relapsed or refractory CLL and MCL. Ublituximab was dosed at 600 and 900 mg in patients with CLL and at 900 mg in patients with MCL, with infusions on Days 1, 8, and 15 of Cycle 1, and on Day 1 of Cycles 2 through 6, with ibrutinib administered daily. As of the data cutoff for the European Hematology Association 2014 meeting, 28 patients were evaluable for safety, with 10 patients evaluable for efficacy.

The combination regimen was well tolerated with infusion related reaction being the most common adverse event reported (29%), followed by diarrhea (21%), rash (21%), and fatigue (18%).

Responses among the 10 evaluable patients are below:

Туре	Pts (n)	CR n (%)	PR n (%)	nPR n (%)	SD n (%)	PD n (%)	ORR n (%)
CLL	7	-	6 (86)	-	1 (14)	-	6 (86)
MCL	3	1 (33)	2 (67)	-	-	-	3 (100)
Total	10	1 (10)	8 (80)	-	-	-	9 (90)

The addition of ublituximab appears to abrogate the ibrutinib related lymphocytosis, with a median 79% decrease in ALC from baseline among patients by Cycle 4, with 3/5 CLL patients for whom data was available showing a normalization of ALC (<4000/uL).

UTX-IB-301

Dated: 31 July 2017 (Ver. 2.5) Page **24** of **85**

PRIMARY OBJECTIVE

• To evaluate the effect of the addition of ublituximab to ibrutinib on antitumor activity, as measured by the overall response rate (ORR = CR + PR) in patients with previously treated CLL with high-risk cytogenetics.

SECONDARY OBJECTIVES

- To evaluate the effect of the addition of ublituximab to ibrutinib on complete response (CR) rate.
- To evaluate the effect of the addition of ublituximab to ibrutinib on the rate of patients achieving minimum residual disease (MRD) negativity.
- To evaluate the effect of the addition of ublituximab to ibrutinib on progression-free survival (PFS), duration of response (DOR), and time to response (TTR).

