11.1 SAMPLE SIZE AND POWER

11.2 GENERAL ANALYSIS CONVENTIONS

Statistical analyses will be conducted by TG Therapeutics or its designee. Statistical analysis will be performed on the intent-to-treat (ITT) population for primary efficacy endpoints and the Treated Population for primary and secondary efficacy endpoints and for safety endpoints.

Baseline is defined as the last measurement for a variable prior to the initial dose of study treatment. Hypotheses will be tested at the 5%, two-sided statistical significance level, unless otherwise specified. Efficacy and safety analyses will be performed using SAS® version 9.2 or higher (SAS Institute, Cary, NC), or comparable software.

All data collected on the eCRF will be listed. Routine data listing or tabulation review during the study conduct will be performed to identify missing data, anomalies, outliers, etc. A complete description of data handling rules and planned statistical analyses is detailed in a separate statistical analysis plan (SAP) prior to conducting any planned analysis.

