11.10.2.1.4 MINIMAL RESIDUAL DISEASE NEGATIVITY RATE

The MRD negativity rate is defined as the proportion of patients who are MRD negative post-baseline. MRD negativity rate is defined as the proportion of the patients in the Treated Population who are MRD negative, excluding any patients who remain on study treatment at the time of the analysis and have a Cycle 1/Day 1 start date less than 6 months from the time of the analyses. For the sake of clarity, the MRD negative analysis will exclude those patients that are too early to evaluate because MRD negativity is only tested for patients on study ≥ 6 months. Patients who drop off study for any reason prior to their 6 month visit will be included in the analysis.

The MRD negativity rate will be compared between treatment groups at the 5%, two-sided statistical significance level using the same methodology as that described in Section 11.10.1 for ORR.

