6.1.2.2 DURATION OF RESPONSE

The Duration of Response (DOR) is defined as the interval from the first documentation of CR or PR to the earlier of the first documentation of disease progression or death from any cause.

The DOR rate will be compared between treatment groups at the 5%, two-sided statistical significance level using stratified log-rank test. The median DOR will be estimated by Kaplan-Meier method, The hazard ratio (HR) with 2-sided 95% confidence interval will be estimated using stratified Cox regression model. The DOR analysis will be performed for responders only (CR/PR) in the ITT population.

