6.1.2.4 MINIMAL RESIDUAL DISEASE NEGATIVITY RATE

MRD negativity rate is defined as the proportion of patients in the Treated Population who are MRD negative, excluding any patients who remain on study treatment at the time of the analysis and have a Cycle 1/Day 1 start date less than 6 months from the time of the analyses. For the sake of clarity, the MRD negative analysis will exclude those patients that are too early to evaluate because MRD negativity is only tested for patients on study \geq 6 months. Patients who drop off study for any reason prior to their 6 month visit and do not have an MRD assessment will be included in the analysis and considered non-responders.

For each treatment group, the number of patients achieving MRD negativity will be divided by the total number of eligible patients (see above paragraph) to yield the proportion responding. The MRD negativity rate will be compared between treatment groups at the 5%, two-sided statistical significance level using the same methodology described in Section 6.1.1.

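### MRD negativity, a listed secondary objective, is tested at 5% two-sided outside the SAP's error control for secondary outcomes, and nothing in the readable text labels the result nominal

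*SAP*

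**What the plan says.** The protocol's secondary objectives (section 4) include this one: "To evaluate the effect of the addition of ublituximab to ibrutinib on the rate of patients achieving minimum residual disease (MRD) negativity". SAP 3.4.2 lists it too.

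Both documents give it a test at a stated level. SAP 6.1.2.4: "The MRD negativity rate will be compared between treatment groups at the 5%, two-sided statistical significance level". Protocol 11.10.2.1.4 sets the comparison at the 5%, "two-sided statistical significance level using the same methodology as that described in Section 11.10.1 for ORR". The protocol's default in 11.2 is the same: "Hypotheses will be tested at the 5%, two-sided statistical significance level, unless otherwise specified".

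The SAP's multiplicity text is listed in the contents as 6.5. In the readable copy it follows directly on 6.2. It makes secondary testing conditional on a significant ORR in the ITT population and names CR rate, DOR and TTR. It then says: "The Hochberg approach will be used to control the type I error rate". The family is closed by number: "The three p-values associated with these three secondary outcomes" are ordered and compared with 0.05, 0.025 and 0.0167. If ORR is not significant, "the secondary efficacy variable defined above will not be formally conducted".

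The 5% wording is not peculiar to MRD. SAP 6.1.2.2 says: "The DOR rate will be compared between treatment groups at the 5%, two-sided statistical significance level using stratified log-rank test". SAP 6.1.2.1 uses the same level for CR. For those two outcomes the multiplicity text replaces the flat 5% with the Hochberg rule.

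**The concern.** MRD has a formal between-arm test at 5%, and the multiplicity text does not include it. Followed as written, the plan lets an MRD result be declared significant on its own 5%, in addition to the 5% already allotted to CR, DOR and TTR. Nothing readable tells the analyst or a later reader that such a result would be nominal.

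At stake is what a significant MRD p-value may be said to show. The SAP has chosen to limit false claims among secondary outcomes. A listed secondary outcome left outside that limit weakens it.

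**Working it through.** **Inputs.** From the documents: ORR, MRD and the secondary family each at 5% two-sided (SAP 6.1.1, 6.1.2.4 and the multiplicity text); three Hochberg members; thresholds 0.05, 0.025 and 0.0167. Assumed, because the documents give none: correlation between test statistics of 0, 0.3, 0.5 or 0.8, equal for all pairs.

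**1. The plan's own thresholds.** Hochberg compares the i-th largest p-value with 0.05/i: 0.05/1 = 0.05, 0.05/2 = 0.025, 0.05/3 = 0.0167. These match the SAP.

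**2. Independent tests, closed form.** With three true nulls, Hochberg rejects nothing if the largest p-value is at least 0.05, the middle one at least 0.025 and the smallest at least 0.01667. Adding the cases with none, one or two p-values between 0.01667 and 0.05:

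- none: 0.95³ = 0.857375
- one: 3 × 0.033333 × 0.95² = 0.090250
- two, not both below 0.025: 3 × 0.95 × (0.033333² − 0.008333²) = 0.002969

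The sum is 0.950594, so the three-member family has error 1 − 0.950594 = 0.0494. With an independent MRD test at 5% added, the chance of at least one false claim is 1 − 0.950594 × 0.95 = 0.0969. Whatever the correlation, if the family holds its own 5%, the sum cannot exceed 0.05 + 0.05 = 0.10.

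**3. Correlated tests, simulation.** Two million draws of two-sided normal tests, all four secondary nulls true, and the ORR condition taken as met:

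| Correlation | Planned family of three | Family of three, plus MRD at 5% | MRD as fourth Hochberg member |
|---|---|---|---|
| 0 | 4.9% | 9.7% | 4.9% |
| 0.3 | 4.8% | 9.2% | 4.7% |
| 0.5 | 4.5% | 8.5% | 4.4% |
| 0.8 | 3.8% | 6.7% | 3.4% |

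The first row agrees with step 2. The last column uses thresholds 0.05, 0.025, 0.0167 and 0.05/4 = 0.0125.

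**4. If ORR is null as well.** The answer depends on how the closing sentence of the multiplicity text is read.

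- *Narrower reading:* it stops only the three listed outcomes. MRD stays testable, and the chance that ORR or MRD is falsely significant is 1 − 0.95² = 0.0975 if independent, and 0.091 at correlation 0.5 by simulation.
- *Broader reading:* it stops every secondary outcome. Overall error is then 5% in this scenario, but MRD is still outside Hochberg, so the third column above still applies once ORR is significant.

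**The case against.** A sponsor may restrict its confirmatory family, and the omission may be deliberate. The two efficacy secondaries left out, MRD and PFS, are those the SAP treats as possibly immature at the ORR analysis: 6.1.2.4 excludes on-treatment patients with less than 6 months since starting, and 6.1.2.5 expects heavy censoring. A reader might infer that a confirmatory MRD claim is planned. The documents do not support that; they announce no such claim. This stands, and it is why a label is enough as the default remedy. It does not remove the point, because the restriction is left to inference. Where the protocol means no formal test it says so, as it does for PFS in 11.10.2.1.6; for MRD it gives a level instead.

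A second objection is that text is missing. The entries for SAP 6.3 and 6.4 are blank in the contents, and the sentence opening the multiplicity text is broken. A rule for MRD could sit there. This limits confidence, but the readable text closes the Hochberg family at three p-values and three thresholds, so any such rule would have to lie outside it.

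Third, the scenario is unfavourable by design. CR is part of ORR, TTR is the time to that same response, and MRD is sampled only in patients in PR or CR. A true ORR effect with no effect on any secondary outcome is therefore unlikely. That is fair. The percentages describe what the testing rule permits, not what this trial is expected to produce.

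**Conclusion.** The point holds. With ORR significant and all four secondary nulls true, the readable plan allows at least one false secondary claim with probability of about 6.7% to 9.7% (correlation 0.8 down to 0), against about 3.8% to 4.9% for the family it set out to control. These figures rest on equal correlations, which are assumed, and on treating the ORR condition as met without modelling ORR's own correlation with the secondary outcomes.

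Two stronger readings go too far. A reader might infer that the plan plainly permits an MRD claim after a failed ORR. That follows only on the narrower reading of the closing sentence, whose wording is ambiguous. A reader might also infer that the plan says nothing on when MRD is analysed. In fact the protocol synopsis, protocol 6.1 and 13, and SAP 3.1 tie the DSMB's review of primary and secondary efficacy analyses to the last patient's first assessment scan, and the MRD definition is framed relative to the time of analysis. Those texts do not fix one date for the MRD p-value, but they bear on it, and no timing defect is claimed here.

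Which population supplies the CR p-value, how PFS is tested and how mature DOR will be are separate questions.

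**What to change.** **Default.** In SAP 6.1.2.4 and 6.5, before database lock, state that the MRD comparison lies outside the multiplicity procedure, that its p-value is nominal, and that it supports no confirmatory claim whether or not ORR is significant. This is a wording change. It takes no power from CR, DOR or TTR; the cost is giving up a formal MRD claim.

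**If a formal MRD claim is wanted.** Test MRD only if ORR is significant in the ITT population, and add it as a fourth Hochberg member with ordered thresholds 0.05, 0.025, 0.0167 and 0.0125. This is sound only if no comparative data have been seen. The SAP is dated 10 December 2020, and the documents do not show whether any had been reviewed by then. The cost is somewhat lower power. An outcome that must succeed as the smallest p-value now needs 0.0125 instead of 0.0167, and MRD moves from a flat 0.05 to a threshold between 0.0125 and 0.05, depending on the other three. The size of the loss depends on effects that the documents do not state, so no power figure is given.

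In either case, reword the closing sentence of the multiplicity text so that it says which secondary outcomes are not formally tested when ORR fails.
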